- DSMC review changed from unblinded to blinded ([10.2](#))
- Addition of scheduled AE review by study staff ([10.3](#))

PROTOCOL SIGNATURE PAGE

A Randomized, Placebo-Controlled Pilot Study of Genistein in Pediatric Cancer Patients
Receiving Myelosuppressive Chemotherapy

INVESTIGATORS' AGREEMENT

I confirm that I have read this protocol and agree to conduct the study as outlined herein. I will also work consistently with the ethical principles that have their origin in the Declaration of Helsinki and that are consistent with good clinical practices and the applicable laws and regulations.

[figure not shown]
Signature:	_____	_____
	[name] Study Chair	Date

Site Name:	_____	
Principle Investigator:	_____	_____
	Signature	Date

	Printed Name	

Instructions to the Investigator: Please sign and date this signature page. File the original signature page in the study file at the site and send a copy of the signed and dated page to the Study Manager.

STUDY DESIGN SCHEMATIC

Chemo: chemotherapy
PE: physical exam
ANC: absolute neutrophil count

SYNOPSIS

Title of Study: A Randomized, Placebo-Controlled Pilot Study of Genistein Supplementation in Pediatric Cancer Patients Receiving Myelosuppressive Chemotherapy	
Study Chair/ UVa Principal Investigator (PI): [name]	
Study center(s): University of Virginia Cancer Center (coordinating center) and participating US sites	
Phase of study: Pilot	Study Initiation: August 2016

Objectives:
 
Primary:
 
 To estimate the effect of supplementation with genistein on the time to neutrophil count recovery following myelosuppressive chemotherapy 
Secondary:
 
 To estimate the effect of supplementation with genistein on short-term side effects of myelosuppressive chemotherapy To estimate levels of the serum markers of inflammation during cycles of chemotherapy given in conjunction with genistein supplementation versus placebo 	

Methodology: This is a multi-center, randomized, double-blind, placebo-controlled crossover study to evaluate the effect of the isoflavone genistein on the short-term untoward effects of myelosuppressive chemotherapy used to treat pediatric cancers. Newly diagnosed cancer patients aged 1 - 21 years will be registered to the study and informed consent will be obtained prior to any study-related procedures. Stratification will be based on length of chemotherapy cycles: 14 days or 21 days. Subjects will be randomized 1:1 to one of two schedules within each stratum:
 
Arm A: Subjects will receive genistein daily throughout chemotherapy Cycles 1 and 2, and placebo during chemotherapy Cycles 3 and 4
 
Arm B: Subjects will receive placebo daily throughout chemotherapy Cycles 1 and 2, and genistein during chemotherapy Cycles 3 and 4
 
The safety and efficacy of genistein will be assessed during each cycle through clinical laboratory tests, cytokine panels, and physical exams. Study supplement compliance will be monitored by use of a subject diary, drug reconciliation, and serum isoflavone levels. Adverse events will be monitored starting on Cycle 1 Day 1 through 30 days following the last day of study supplementation (genistein/placebo). Serious adverse events will be collected through 6 months post-study intervention.
	
Number of subjects (planned): Up to 50 subjects will be accrued to obtain 44 eligible subjects.	

Main Eligibility Requirements:
 
Inclusion criteria:
 
 New diagnosis of a solid tumor or lymphoma, with histologic verification of malignancy Age 1 - 21 years at the time of diagnosis Able to tolerate enteral medication administration Performance score minimum requirement ≥ 50 on Karnofsky/Lansky scale Planned chemotherapy regimen involves at least four consecutive cycles of chemotherapy that is known to be myelosuppressive 
Exclusion criteria:
 
 Known allergy to soy or any soy-based food or supplement Pre-existing neutropenia or neutrophil qualitative or quantitative disorder Pre-existing cytopenia or bone marrow failure syndrome Subject will not receive myelosuppressive chemotherapy Current acute or chronic leukemia diagnosis Enrolled on another therapeutic or supportive care clinical trial within the last 30 days Secondary malignancy 	

Investigational intervention:

- Genistein: 30 mg/day, oral tablets
- Placebo: oral tablets

Both genistein and placebo tablets will be provided by DSM Nutritional Products Europe Ltd, Switzerland.

Other study intervention(s): The chemotherapeutic regimen for each subject will be determined by the treating physician and must contain a combination of at least two agents from the following list during each of the four cycles administered in this study: actinomycin, carboplatin, cisplatin, cyclophosphamide, daunorubicin, doxorubicin, etoposide, ifosfamide, topotecan.

Criteria for evaluation (i.e. endpoints):

Efficacy: To evaluate the effectiveness of genistein administration during myelosuppressive chemotherapy, the following endpoints will be compared between genistein cycles and placebo cycles:

Primary endpoint:

- Duration of grade 4 neutropenia, defined as an absolute neutrophil count (ANC) of < 500 cells/ μ l

Secondary endpoints (per cycle):

- Severity of neutropenia
- Duration of grade 4 neutropenia during hospital admissions for febrile neutropenia
- Frequency and duration of unplanned hospital admissions due to (an) adverse event(s)
- Days with fever (temperature > 101.5° F, or > 100° F more than once in a 24-hour period)
- Incidence and severity of infections
- Duration of antimicrobial agent use
- Duration and severity of oral mucositis
- Duration and severity of peripheral motor neuropathy (in subjects receiving vincristine)
- Incidence and severity of hearing impairment and tinnitus (in subjects receiving a platinum-based chemotherapy agent)
- Number of days delayed and percent reduction of full, planned doses of anti-neoplastic agents due to (an) adverse event(s)
- Incidence of primary and secondary G-CSF use
- Number of required blood product transfusions
- Cytokine, growth factor, C-reactive protein, and homocysteine levels as well as erythrocyte sedimentation rates

Safety: Safety will be assessed by incidence and severity of AEs and changes in physical examinations.

Statistical methods:

Graphical and repeated measure models will be used to describe the complete pattern of ANC over all four cycles. Between group (e.g. Cycles 1 & 2) and crossover differences (Cycles 1 - 4) form the structure for treatment comparisons. Repeated measure models will be used to assess differences in raw ANC, daily ANC, days with fever, duration of hospitalization, and duration of antimicrobial use for subjects admitted with febrile neutropenia. The Cochran–Mantel–Haenszel test statistics will be used in the analysis of stratified categorical data. The Cochran–Mantel–Haenszel test will be used to compare grade and repeated measure models for duration of mucositis between cycles containing genistein versus placebo. Safety data will be summarized and compared during genistein versus placebo cycles.

TABLE OF CONTENTS

SUMMARY OF CHANGES FROM PREVIOUS VERSION	ii
PROTOCOL SIGNATURE PAGE	iii
STUDY DESIGN SCHEMATIC	iv
SYNOPSIS	v
1 BACKGROUND AND RATIONALE	1
1.1 Study Synopsis	1
1.2 Background	1
1.2.1 Toxicities Associated With Chemotherapy for Pediatric Cancers	1
1.2.2 Anti-cancer/Anti-Inflammatory Effects of Soy Isoflavones	2
1.2.3 Genistein Reduces Chemotherapy-Induced Side Effects	3
1.3 Study Design and Rationale	4
2 STUDY OBJECTIVES	6
2.1 Primary Objectives	6
2.1.1 To estimate the effect of supplementation with genistein on the time to neutrophil count recovery following myelosuppressive chemotherapy	6
2.2 Secondary Objectives	6
2.2.1 To estimate the effect of supplementation with genistein on short-term side effects of myelosuppressive chemotherapy	6
2.2.2 To estimate levels of the serum markers of inflammation during cycles of chemotherapy given in conjunction with genistein supplementation versus placebo	6
3 SUBJECT ELIGIBILITY	7
3.1 Inclusion Criteria	7
3.2 Exclusion Criteria	8
3.3 Enrollment Exceptions	8
4 TREATMENT PLAN	9
4.1 Subject Status Definitions	9
4.2 Recruitment	10
4.3 Informed Consent	10
4.4 Registration	10
4.5 Randomization or Arm Assignment	11
4.6 Unblinding	11
4.7 Dosage and Administration	11
4.7.1 Chemotherapeutic Regimen	11
4.7.2 Genistein/Placebo Supplementation	11
4.7.3 Treatment Delays	12

4.7.4	Dose Modifications	12
4.8	Concomitant Medications/Treatments	13
4.8.1	Prohibited Medications	13
4.8.2	Concomitant Medications	14
4.9	Discontinuation of Protocol Therapy	14
4.10	Withdrawal from Study	15
5	SUPPLEMENT INFORMATION	16
5.1	Genistein	16
5.1.1	Chemical Name	16
5.1.2	Other Names	16
5.1.3	Classification	16
5.1.4	Molecular Formula	16

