1.2 Background

1.2.1 Toxicities Associated With Chemotherapy for Pediatric Cancers

While cure rates for pediatric cancers have steadily improved over the last several decades, toxicities associated with cancer therapy continue to cause significant morbidity and mortality [1, 2]. Serious side effects of chemotherapy and radiation are common and are thought to be due to a variety of factors, including depletion of glutamine and glutathione, free radical generation, cytokine release, and oxidative damage [1, 3-9]. Unlike certain targeted anti-cancer agents, most chemotherapeutic drugs have nonspecific mechanisms of action that damage both normal tissue and cancer cells [1]. Similarly, the mechanism of action of radiation is nonspecific and can cause oxidative DNA damage to normal tissues that are within the radiation field [1]. These nonspecific effects of chemotherapy and radiation tend to be more severe in tissues that contain rapidly dividing, mitotically active cells such as those found in the bone marrow [1]. Myelosuppressive regimens cause a predictable decline in peripheral blood cell counts, usually 7 - 10 days after exposure to therapy. Highly-suppressed absolute neutrophil counts during this period put patients at an elevated risk for serious infection [10]. The standard of care at most institutions is to admit neutropenic patients with fever to the hospital and treat with empiric intravenous broad-spectrum antibiotics until their febrile neutropenia resolves. This is due to the high mortality associated with serious bacterial infections in this population, reported to be around 1% [11, 12]. Such patients also often require packed red blood cell and platelet transfusions for chemotherapy-induced anemia and thrombocytopenia, respectively, which are

associated with hemolytic transfusion reactions and transfusion-transmitted infections. Other common acute toxicities due to cancer treatment include mucositis caused by chemotherapy and radiation as well as neurotoxicity due to vincristine and other tubulin-inhibiting chemotherapeutic agents [13-15].

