6.3 Treatment Phase Assessments (Cycles 1 – 4)

Investigators should maintain good clinical practice and perform standard of care assessments and procedures per local institutional guidelines. In addition, the following list of study-specific assessments must be performed once a patient enters the Treatment Phase. All visits and assessments must be completed within \pm 72 hours of the milestone date unless otherwise specified.

- The following will be performed for the purposes of assessing clinically significant AEs. AEs found prior to the first study supplement dose must be reported as baseline conditions. See [Section 9](#) and the Procedure Manual for more information about AE reporting.
 - Chemistry/metabolic liver function labs on Day 1 of each cycle: must include serum creatinine, total bilirubin, AST, and ALT (Procedure Manual)
 - CBC with differential on Day 1 of Cycles 2, 3, and 4, and at weekly visits: must include hemoglobin, hematocrit, platelet count, total white blood cell count and automated white blood cell differential (manual differential if automated not available) (Procedure Manual). See below for additional requirements for ANC reporting.
 - Full physical exam on Day 1 of each cycle and a symptom-directed physical exam at each of the weekly visits ([Section 6.2.1](#))
 - The Pre-treatment and Cycle 1 Day 1 physical exams may be combined performed \leq 72 hrs. prior to Cycle 1 Day 1.
 - Subjects receiving vincristine must be assessed for vincristine toxicity in the form of peripheral motor neuropathy.
 - Audiograms for subjects receiving a platinum-based chemotherapy agent at 0 - 4 days prior to Day 1 of Cycles 2, 3, 4, and 0 - 4 days prior to the last day of Cycle 4. Assess hearing impairment and tinnitus.
- ANCs must be obtained as follows:
 - The ANC must include both neutrophils and bands. The following equation is recommended:
$$\text{ANC} = \text{WBC} \times 1000 (\% \text{ Neutrophils} + \% \text{ Bands})$$
 - Obtain on Day 1 of Cycles 2, 3, 4 and at weekly visits

- Once ANC levels begin to decrease, ANC must be determined at least twice weekly (≤ 96 hours between blood collection) until ANC recovers to ≥ 500 cells/ μ L, then switch to weekly testing in the following situations:
 - If nadir is < 500 cells/ μ L, begin once ANC ≥ 500 cells/ μ L, OR
 - If nadir is ≥ 500 cells/ μ L, begin once ANC has increased by 50% above nadir

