- If ANC is < 500 cells/ μ L at any point after beginning weekly testing, resume twice weekly testing until ANC ≥ 500 cells/ μ L.
- ANC will be obtained daily during any admission for febrile neutropenia.
- All ANC values will be reported.
- Serum CRP, homocysteine, and ESR: Report raw data collected on Day 1 of Cycles 2, 3, 4, and the last day of Cycle 4
- Cytokine Panel and Isoflavone Panels: Draw and process specimen per the Procedure Manual on Day 1 of Cycles 1, 2, 3, 4, and the last day of Cycle 4
- Weight and height on Day 1 of each cycle
- The following **target AEs** must be assessed and the maximum grade reported for each cycle in addition to standard AE/SAE reporting ([Section 9](#)):
 - Neutropenia
 - Febrile neutropenia, with maximum associated temperature per cycle
 - Fever, including number of days per cycle, for temperatures $> 101.5^{\circ}$ F, or $> 100^{\circ}$ F more than once in a 24-hour period (report maximum temperature)
 - Infections and Infestations: Maximum grade for any AE listed in this CTCAE category. Infections meeting the AE reporting threshold must be listed individually.
 - Oral mucositis
 - Tinnitus (subjects receiving platinum-based chemotherapy only)
 - Hearing impairment (subjects receiving platinum-based chemotherapy only)
 - Peripheral motor neuropathy (subjects receiving vincristine only)
- Report per cycle:
 - Study supplement:
 - Total number of tablets taken

- Subject compliance with study medication dosing as determined by self-reported administration reports and supplement reconciliation
- Reason for dose change, if applicable. Any AE(s) precipitating a dose reduction must be reported even the minimum AE reporting threshold is not otherwise met ([Section 9.2](#)).
- Anti-neoplastic treatment delay(s):
 - Total number of days delayed from planned schedule
 - Cause for delay: AE, or reason other than AE
- Anti-neoplastic agent dose reduction(s):
 - Delayed agent(s)
 - Planned dose(s)
 - Actual dose(s)
 - Cause for dose change: AE, or reason other than AE
- All unplanned or prolonged hospitalizations due to (an) AE(s) ([Section 9.1.9](#)):
 - Date of admission or start of prolongation and discharge date
 - Causes/diagnoses precipitating hospitalization or prolonged hospitalization
- Concomitant medication review at each scheduled visit for the following:

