7.2 Secondary Endpoints (per cycle)

“Incidence” refers to both the frequency of an event per subject and the number of affected subjects in this study.

- **Severity of neutropenia**
- Duration of **grade 4 neutropenia during hospital admissions for febrile neutropenia**
- Frequency and duration of unplanned or prolonged **hospitalizations** due to (an) AE(s) ([Section 9.1.9](#))
- Days with **fever** (temperature > 101.5° F, or > 100° F more than once in a 24-hour period)
- Incidence and severity of **infections**
- Duration of **antimicrobial use**
- Duration and severity of oral **mucositis**
- Duration and severity of **peripheral motor neuropathy** (in subjects treated with vincristine)
- Incidence and severity of **hearing impairment** and **tinnitus** (in subjects treated with a platinum-based chemotherapy agent)
- Number of days of **delays and percent reduction of full planned doses of anti-neoplastic agents due to (an) AE(s)**
- Incidence of primary and secondary **G-CSF use**
- Number and cause of required **blood product transfusions**
- **Serum cytokine levels:**
 - G-CSF, granulocyte-macrophage colony stimulating factor (GM-CSF), interferon- α (IFN- α), IFN- γ , IL-1 β , IL-1 receptor antagonist (IL-1RA), IL-2 receptor (IL-2R), IL-4, IL-5, IL-6, IL-7, IL-8, IL-10, IL-12, IL-13, IL-15, IL-17, TNF- α .

- **Chemokines:** eotaxin, IFN- γ induced protein 10 (IP-10), monocyte chemotactic protein 1 (MCP-1), monokine induced by IFN- γ (MIG), macrophage inflammatory protein 1- α (MIP-1 α), MIP-1 β , Regulated upon Activation Normal T cell Expressed and presumably Secreted (RANTES).
- **Serum growth factor levels:** epidermal growth factor (EGF), fibroblast growth factor-basic (FGF-basic), hepatocyte growth factor (HGF), vascular endothelial growth factor (VEGF)
- **Serum CRP levels, homocysteine levels, and ESRs**

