8.4 Data Analyses Plans

Graphical and repeated measure models will be used to describe the complete pattern of ANC over all four cycles. Between-group (Cycles 1 & 2) and crossover differences (Cycles 1 - 4) form the structure for treatment comparisons. Repeated measure models

will be used to assess differences in raw ANC, daily ANC, days with fever, duration of hospitalization, and duration of antimicrobial use for subjects admitted with febrile neutropenia. The Cochran–Mantel–Haenszel test statistics will be used in the analysis of stratified categorical data such as neutropenia grades (severe: ≤ 100 cells/ μl ; moderate: ≤ 500 cells/ μl ; mild: ≤ 1000 cells/ μl) and filgrastim (G-CSF) usage. For duration and severity of mucositis and peripheral motor neuropathy, detailed physical examinations will be documented at each weekly physical exam. Grading (grade 1 - 5) will be performed according to the [CTCAE](#) guidelines, version 4.0. The Cochran–Mantel–Haenszel test will be used to compare grade and repeated measure models for duration of mucositis between cycles containing genistein versus placebo.

Number of subjects who experience hearing impairment and tinnitus will be summarized by treatment for each cycle. The number of required blood product transfusions, both packed red blood cells and platelets, will be documented and compared during genistein and placebo cycles using repeated measure models. Reporting will be in the form of total ml/kg body weight infused of red blood cells and platelets. Criteria for transfusion are listed in [Section 4.8.2](#).

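### The febrile-neutropenia admission endpoint sets no score for a cycle without an admission, and the wording of Section 8.4 points to a comparison restricted by a post-randomisation event

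*Combined protocol and SAP*

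**What the plan says.** - **Endpoint.** The Synopsis lists "Duration of grade 4 neutropenia during hospital admissions for febrile neutropenia" among the per-cycle secondary endpoints, and Section 7.2 repeats "grade 4 neutropenia during hospital admissions for febrile neutropenia". The Synopsis adds that "the following endpoints will be compared between genistein cycles and placebo cycles".
- **Scoring rule.** Neither place gives a value for a cycle without an FN admission. For its own awkward case, a nadir that never falls below 500, Section 7.1 does state how the primary endpoint is scored.
- **Analysis.** Section 8.4 does not name this endpoint. The nearest text is a list of repeated-measures analyses covering raw ANC, daily ANC, fever days and length of hospital stay, which ends with "duration of antimicrobial use for subjects admitted with febrile neutropenia". It is not clear whether the closing words restrict the whole list or only its last item.
- **Sampling.** Section 6.3 says "ANC will be obtained daily during any admission for febrile neutropenia". Outside such admissions, once counts begin to fall, "ANC must be determined at least twice weekly". Daily ANC is therefore required only in admitted cycles.
- **Route to admission.** Section 1.2.1 describes usual practice at most institutions: "admit neutropenic patients with fever to the hospital and treat with empiric intravenous broad-spectrum antibiotics until their febrile neutropenia resolves".
- **Hypothesis.** Section 1.1 expects fewer short-term treatment side effects in genistein cycles.

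**The concern.** FN admission happens after randomisation and lies on the pathway that genistein is meant to alter. If only admitted cycles are compared, the two sets of cycles are no longer those that randomisation balanced. If genistein prevents some admissions, the genistein cycles that remain may differ in severity from the placebo cycles that remain.

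Three consequences are possible for this endpoint. A fall in admissions may hardly show. A real shortening of neutropenia may look smaller than it is. If the prevented admissions are mainly those with short neutropenia, the mean among the remaining admissions can rise.

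As admission normally follows fever, the count also leaves out grade 4 days before admission. The measure therefore reflects time spent neutropenic in hospital, not the length of neutropenia.

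**Working it through.** **The plan's own figure.** None is given for this endpoint. The only power statement (Section 8.2) concerns day of recovery: 22 per group, one-sided 5% Mann-Whitney-Wilcoxon test, Poisson means 16.25 and 13.25. Simulation with 20,000 samples gives 79.7% with and 80.0% without continuity correction, so the stated 80% or so reproduces. This point does not touch it.

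**Assumed inputs.** The documents give no FN rate, fever hazard or duration of neutropenia, so all of these are assumptions:
- grade 4 duration D: gamma, mean 6 days, shape k = 2 or 4;
- time from onset of grade 4 neutropenia to fever T: exponential, hazard h = 0.05 or 0.15 per neutropenic day;
- admission at fever if T < D, lasting until ANC recovers, so an admitted cycle scores D − T.

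**Formulas.**
- Proportion of cycles admitted: p = 1 − (1 + 6h/k)^(−k)
- Mean with 0 for no admission: Z = 6 − p/h
- Mean among admitted cycles only: C = Z/p

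Example, k = 2 and h = 0.05: p = 1 − 1.15^(−2) = 0.244; Z = 6 − 0.2439/0.05 = 1.12; C = 1.12/0.244 = 4.60. With h halved to 0.025: p = 1 − 1.075^(−2) = 0.135; Z = 6 − 0.1347/0.025 = 0.61; C = 4.55.

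**1. Fever hazard halved, neutropenia unchanged.**

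| k | h | Cycles admitted | Admitted-only mean C (days) | Zero-filled mean Z (days) |
|---|---|---|---|---|
| 2 | 0.05 | 24% → 13% | 4.60 → 4.55 (−0.05) | 1.12 → 0.61 (−45%) |
| 2 | 0.15 | 52% → 33% | 4.78 → 4.65 (−0.12) | 2.50 → 1.55 (−38%) |
| 4 | 0.05 | 25% → 14% | 3.89 → 3.82 (−0.07) | 0.98 → 0.52 (−46%) |
| 4 | 0.15 | 56% → 35% | 4.13 → 3.95 (−0.18) | 2.29 → 1.37 (−40%) |

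A separate model, with 7-day mean neutropenia and a daily admission risk of 6% against 3%, agrees. Admissions fall from 34% to 19%, the admitted-only mean goes from 5.1 to 5.0 days, and the zero-filled mean from 1.73 to 0.94.

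**2. Neutropenia truly shortened, hazard unchanged.** The form of the shortening matters.
- Flat 3 days off each episode, floored at 0 (true mean reduction 2.7 to 2.9 days): the admitted-only mean falls 0.56 to 1.13 days, or 21-39% of the true effect.
- The same mean reduction applied proportionally: it falls 1.9 to 2.2 days, or 66-82%.
- In the separate model, with mean neutropenia cut from 7 to 5 days, it falls from 5.10 to 3.75: 1.35/2 is about 68%.

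**3. Only short episodes prevented.** If every episode under 4 days is abolished and longer ones are untouched, mean grade 4 days fall from 6.0 to 5.1-5.2 and admissions from 24-56% to 20-46%. The admitted-only mean nevertheless rises by 0.4 to 0.9 day, while the zero-filled mean falls by 5-7% (for example 1.12 to 1.06).

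**4. Subjects with a value on both treatments.** A complete-case within-subject difference needs an admission in both two-cycle periods. With independent cycles the expected number is 44 × [1 − (1 − p)²]². At p = 0.2 this is 44 × 0.36² = 5.7. At p = 0.3, 0.4 and 0.5 it is 11.4, 18.0 and 24.8.

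**The case against.** The strongest reply is that 0 is the natural value of a per-cycle duration when no admission occurs. The endpoint is listed per cycle, and the Synopsis compares genistein with placebo cycles, not admitted cycles. On that reading the proposed scoring is already intended. The admitted-subjects phrase in Section 8.4 refers to subjects rather than cycles, may attach only to antimicrobial use, and does not name this endpoint. This stands to the extent that the documents are silent. A reader might infer that the endpoint has no value in other cycles by definition; the text does not say so. But the only nearby analysis wording, and the restriction of mandatory daily ANC to FN admissions, both point to the restricted reading. The two readings can also give materially different answers.

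A reader might also infer that prevented admissions would be invisible to the trial. They would not. Frequency and duration of unplanned hospitalisations for adverse events, days with fever, infections and antimicrobial duration are separate endpoints, and FN is recorded as a target event in each cycle. The hospitalisation endpoint covers all adverse events rather than FN alone, so it does not replace a clear rule here.

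The primary endpoint, as worded in either the Synopsis or Section 7.1, does not depend on admission. An inpatient measure beside it is a legitimate secondary endpoint.

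The size depends on the scenario. Quoting only the 21-39% attenuation would present the flat-shift model as the whole range. Calling the endpoint one that reads as harm would rest on selective prevention of short episodes, which no section predicts. The paired counts assume complete-case analysis and independent cycles; the repeated-measures models in Section 8.4 need not drop subjects who have values on one treatment only.

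Finally, scoring 0 does not recover neutropenic days before admission. That is correct, and it is why the label has to change as well.

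**Conclusion.** The point holds in a limited form. The endpoint counts only in-admission days, has no stated score for cycles without an FN admission, and sits beside analysis wording that points to an admitted-only comparison. Such a comparison conditions on a post-randomisation event that treatment may change.

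Under the assumed inputs, a halved fever hazard moves the admitted-only mean by 0.05 to 0.18 day, while the zero-filled mean falls 38-46%. A true shortening of neutropenia shows at between 21% and 82% of its size, depending on its form. Reversal of sign is possible but needs mainly short episodes to be prevented. All of these figures rest on assumed durations and hazards.

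The issue is confined to one secondary endpoint of a pilot. It is worth settling before analysis because a pilot is meant to supply usable estimates, and the two permitted readings can disagree greatly in size and, in the selective case, in direction.

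**What to change.** In the Synopsis, Section 7.2 and Section 8.4:

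- Define the endpoint as days per cycle with ANC < 500 while hospitalised for FN, scored 0 in a treated cycle without such an admission. A cycle not given or not observed stays missing rather than 0.
- Analyse it in all randomised subjects and cycles, and name it in Section 8.4 with a count or rank-based model.
- Label it a hospital-burden measure, not a measure of how long neutropenia lasts.
- Report the proportion of cycles with an FN admission, by treatment, beside it.
- Call any summary restricted to admitted cycles descriptive.

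The cost is wording only. Section 6.3 already requires all ANC values and the dates and causes of unplanned admissions to be reported. The downside is an outcome with many zeros, hence the choice of model. If length of neutropenia is also wanted as days with ANC < 500 from all reported values, a rule for the days between samples is needed, because counts outside FN admissions may be up to 96 hours apart.
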